The purpose of the present funding opportunity (PAR-17-156) is to begin to evaluate, with a high degree of fidelity, ECs as a potential means of reducing smoking-related risks and to provide information on the use and effects of JUUL; it is also meant to be completed quickly (two-year study). In order to successfully execute our research plan, we will conduct the present study with a quitline (QL) population, characterized by high levels of nicotine dependence, low socioeconomic and educational attainment, and high levels of substance use and mental health disorders—priority populations for tobacco control. QLs provide ready access to a large number of tobacco users, as well as infrastructure for delivering and testing study interventions. Our team has successfully carried out large-scale QL recruitment (e.g., 2,000 smokers in 8 months) for past trials. QLs are potentially the best real-world platform to quickly and with sufficient statistical power, meaningfully examine smokers' willingness to switch to JUUL and its downstream effects on smoking and health.

Therefore, the overall aim of the proposed study is to evaluate the provision of JUUL versus NRT on smoking behavior, product use patterns and continued use, and iCO, a biomarker of toxicant exposure, among a sample of recent QL treatment failures. We will randomly assign 420 smokers to JUUL or treatment as usual, combination nicotine replacement therapy control (NRT). All participants will receive three calls from QL coaches and JUUL and NRT will be provided at no cost for 8 weeks. The final follow-up will occur 12-weeks post baseline.

Aim 1: To assess JUUL vs. NRT on product switching/substitution, craving/withdrawal, abuse liability, number of cigarettes smoked, and perceived nicotine dependence. *Hyp 1a: Complete product substitution (vs. partial or no substitution) will occur at a significantly higher rate among smokers randomized to the JUUL compared to those randomized to NRT at 8 and 12-week follow-ups. Hyp 1b: Compared to those randomized to NRT, JUUL participants will report less nicotine craving, fewer nicotine withdrawal symptoms, smoke fewer cigarettes per day, and higher perceived nicotine dependence.*

Switching to a Vaping Device: Evaluating Risk Reduction among Quitline Treatment Failures

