Aim 2: To evaluate changes in iCO, a biomarker of tobacco constituent exposure. *Hyp 2: The degree of change will be directly associated with the degree of substitution with J or NRT—greater levels of substitution will confer a larger decrease in exposure to harmful constituents.*

Aim 3: To evaluate which EC device characteristics and perceived effects influence complete (vs. partial or no substitution). *Hyp 3a: Participants reporting higher product satisfaction, including product durability, battery life, “throat hit”, taste, craving reduction, improved mood with use, and ease of use, will achieve higher rates of complete substitution.*

B. Significance

Quitting is Difficult for Many Smokers

Nearly 50% of smokers make a quit attempt each year, but less than 5% remain abstinent for 3-12 months after quitting.¹⁻³ As a result, the prevalence of cigarette smoking among adults in the U.S. remains disturbingly high.¹ Current cessation products and counseling are effective, doubling a smokers chances of long-term abstinence, but are not universally effective for all smokers, and most smokers fail to quit on their first attempt.⁴⁻⁷ Moreover, a significant minority of smokers finds it very difficult to quit smoking with current FDA-approved products.⁸ To prevent these individuals from returning to smoking following a failed quit-attempt, offering them other less toxic and carcinogenic forms of nicotine would potentially offer a significant health benefit over smoking. This approach is consistent with a tobacco harm reduction model, which asserts that it is preferable to reduce tobacco-related harm by having smokers switch to less toxic products when complete cessation is unobtainable⁹; electronic cigarettes maybe one such product.

The Promise of Electronic Cigarettes: Overview and Limitations of the Available Research

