Sociodemographic data will assess participant age, sex, marital status, ethnicity, employment status, occupation, years of education, and socioeconomic status. Tobacco use history will assess years of smoking, age of smoking onset, average number of cigarettes per day, number and recency of previous 24-hour quit attempts, number of smokers in the household, prior use of nicotine replacement therapy and other stop smoking medications, and history of receiving smoking cessation counseling, and cigarette and EC expectance effects. It will also assess tobacco type, brand, frequency, quantity, and duration of use all of nicotine/tobacco products including cigars, cigarillos, little cigars, pipe tobacco, chewing tobacco, snuff, snus, EC, combustible tobacco hookah, and dissolvable tobacco. Complete Substitution will be defined as ≥7 days with no more than 1 conventional cigarette smoked (assessed via EMAs), daily exhaled carbon monoxide of ≤6 ppm as measured by iCO (see biomarker measures below), and reported use of ECs over the same 7-day period.

Switching to a Vaping Device: Evaluating Risk Reduction among Quitline Treatment Failures

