TLFB		x	x	Cigarette/Vape Availability
Motivation Rulers – 8 to 12		x	x	Cessation Motivation
Cigarette Purchase Task		x	x	Smoking Restriction
iCO		x	x	Vaping Restriction
				Cigarette Reward Value
				Alcohol Use

* Daily Diary EMAs also include Random EMA items

E. Statistical Methods

1. Power Analysis

Complete substitution of combustible cigarettes for EC products is the primary outcome of the study, as the rate of product substitution will likely drive the outcomes for all of the other aims. We will compare the proportion of participants with complete substitution in the JUUL vs. NRT at the end of the product trial phase (8-week follow-up) using the Fisher's exact test. There are no direct data available on which we can base sample size estimates for the proposed study. The closest estimate for the JUUL arm was based on the 6 week, 35% switch rate for JUUL in a pilot study of a community sample of African American/Black smokers ([name], personal communication). Likewise, we estimate that the percent of complete substitution will be 35%. For the NRT, the closest estimate was the 4 week, 30% abstinence rate for preferred NRT product among a sample of smokers motivated to quit smoking¹⁵⁶; however, we will conservatively assume a NRT substitution rate of 20% since participants will have tried NRT previously and were not successful. We will assume an attrition rate of 20%. Assuming 20% attrition among a total of 420 participants (186/group), will allow 300 participants to be analyzed in the final sample. A sample size of 300 will provide >80% power to detect a difference in complete substitution between JUUL and NRT groups for a two-sided .05 level chi-squared test. It is important to note that this sample size is deliberately conservative, as it does not assume the availability of repeated outcome measures that will be taken throughout the study. By choosing models that utilize longitudinal data, we will further increase the power to detect differences between arms

2. Data Analytic Plan

Statistical analyses will be performed using SAS 9.4. P-values less than .05 will be considered statistically significant. Baseline demographics and smoker characteristics will be summarized by groups (JUUL and NRT), as appropriate. Continuous variables will be presented as mean \pm SD and compared among the 2 groups using ANOVA test. Categorical variables will be presented as counts and proportions and compared among the 2 groups using the chi-squared test.

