Switching to a Vaping Device: Evaluating Risk Reduction among Quitline Treatment Failures

Aim 1: The focus of aim 1 is the examination of differential levels of (Hyp 1a) substitution between JUUL and NRT, and (Hyp 1b) reported nicotine craving, withdrawal symptoms, number of cigarettes smoked per day, product abuse liability, and nicotine dependence, between JUUL and NRT. *Hypothesis 1a:* Complete substitution rates, at the 8 and 12 week follow-ups, will be compared between JUUL and NRT arms using logistic regression analysis, adjusting for baseline variables such as age, gender, number of cigarettes per day and/or randomization stratification factors. The GEE model will be performed for the repeated measure analysis of complete substitution rate across multiple visits. *Hypothesis 1b:* If needed, we will apply a normalizing transformation to the response measure (e.g., taking the logarithm of cigarettes per day) before proceeding with the analysis, as a means of removing the effects of potential outliers. We will examine changes in each outcome over time across the two groups using linear mixed model (LMM) regression analysis. We will employ a random intercept or slope parameter, as appropriate, and model the covariance structure for the repeated outcome measures, while accounting for baseline value of the outcome and potential confounders (including any variables not equally distributed between groups). Modeling is done using a likelihood-based approach and thus makes use of all available data (on the intention-to-treat (ITT) sample) to produce consistent estimates of the regression parameters. Contrast estimates comparing group effects over time will be used as measure of effect. A similar approach will be used to explore the EMA data collected.

Aim 2: The focus of aim 2 is the examination of changes in a biomarker of toxicant exposure. *Hypothesis 2:* We will examine changes in iCO, a biomarker of toxicant exposure, and EMA data using the methods outlined in Hypothesis.

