Aim 3: The focus of aim 3 is (Hyp 3a) to determine which EC device characteristics and perceived effects are associated with complete (vs. partial or no) substitution. *Hypothesis 3a:* We will examine whether changes in EC device characteristics and perceived effects obtained by EMA over time differ between those who achieve complete (vs. partial or no) substitution using linear mixed model (LMM) regression analysis. We will employ a random intercept or slope parameter, as appropriate, and model the covariance structure for the repeated outcome measures, while accounting for potential confounders. We will use similar methods to explore return to smoking in those who report complete substitution at any time during the study.

3. Missing Data

In the event of missing data, we will contact participants immediately. If a participant drops out, we will attempt to gather follow-up information by calling the study phone and trying to reach the participant through other provided contact information. However, if a participant refuses to be contacted or loses contact with the investigators, we will censor data at point of loss. Two statistical approaches will be used to handle missing data. First, we will use inverse probability weighting with propensity scores. This is a two-step procedure in which we first model the probability of missingness as a function of baseline covariates and previous outcomes. Next, the inverse of the resulting predicted probabilities (from the logistic regression model) will serve as weights in our proposed model of the response. We will compare these results to a more conservative ITT approach as a final step.

Switching to a Vaping Device: Evaluating Risk Reduction among Quitline Treatment Failures

F. Gender/Minority/Pediatric Inclusion for Research

1. Inclusion of Women and Minorities

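### Complete Substitution, the primary outcome, requires reported e-cigarette use and has no NRT counterpart, so an NRT participant who stops smoking without vaping is scored a failure

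*Combined protocol and SAP*

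**What the plan says.** Section D.3 (Measures) holds the only operational definition of Complete Substitution in the text available to this review. Its parts are joined by *and*: at least seven days with at most one cigarette by EMA, daily iCO of 6 ppm or less, "and reported use of ECs over the same 7-day period". There is no arm-specific version.

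Section E.1 (Power Analysis) states that "Complete substitution of combustible cigarettes for EC products is the primary outcome of the study" and compares it between arms at week 8 by Fisher's exact test. Hypothesis 1a in section A reads "Complete product substitution (vs. partial or no substitution) will occur at a significantly higher rate among smokers randomized to the JUUL", at weeks 8 and 12. In section E.2 the rates "will be compared between JUUL and NRT arms using logistic regression analysis".

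The NRT arm is mailed patch and lozenge (D.1) and receives cessation counselling (D.2, Coach Calls). The request to switch to the e-cigarette is addressed to JUUL participants (D.2, Randomized Product Trial Phase; JUUL Education and Counseling).

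Other text treats substitution with NRT as something that can occur. Hypothesis 2 says "The degree of change will be directly associated with the degree of substitution with J or NRT", and section G.6 describes participants trying to substitute either product. In E.1 the NRT planning rate starts from "the 4 week, 30% abstinence rate for preferred NRT product", after which "we will conservatively assume a NRT substitution rate of 20" per cent. None of these places says how an NRT participant is scored.

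**The concern.** In the NRT arm, success needs smoking cessation plus use of a type of product that arm is not given. A participant who meets the cigarette and CO criteria on the assigned patch and lozenge fails unless he or she also vapes. A JUUL participant who gives up both cigarettes and JUUL fails too, but the rule bears mainly on the NRT arm.

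Hypothesis 1a is a between-arm superiority test. With this endpoint, JUUL can appear superior when smoking does not differ between the arms, or even when NRT does better. If an NRT counterpart was intended, the text does not state it, and two analysts following the documents could report different primary results.

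The planning rates also refer to different things. The JUUL figure of 35% is a switch rate, while the NRT figure of 20% is a reduced abstinence rate that has nothing to do with vaping.

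**Working it through.** **Inputs.** From E.1: JUUL 35%, NRT 20%, two-sided 0.05, 300 analysed, taken as 150 per arm. Assumed, because the documents give no figure: the share of abstainers in each arm who report e-cigarette use.

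**The plan's own figure.** At 35% versus 20% with 150 per arm, power is 83.2% by the pooled chi-squared test and 80.3% by Fisher's exact test. The stated power above 80% reproduces.

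**Method.** Let p be true abstinence (cigarette and CO criteria met) and v the share of abstainers who vape, with subscripts J and N for the arms. The scored rate is m = p × v. The probability that JUUL is declared superior is the sum of Bin(x; 150, mJ) × Bin(y; 150, mN) over all outcomes with x > y and two-sided Fisher p < 0.05.

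**(a) Equal true abstinence, 20% in both arms**

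| vJ | vN | Scored JUUL vs NRT | JUUL declared superior |
|---|---|---|---|
| 100% | 0% | 20% vs 0% | >99.9% |
| 100% | 20% | 20% vs 4% | 99.2% |
| 100% | 50% | 20% vs 10% | 62.9% |
| 100% | 75% | 20% vs 15% | 16.4% |
| 100% | 100% | 20% vs 20% | 1.8% |
| 80% | 20% | 16% vs 4% | 93.2% |
| 80% | 50% | 16% vs 10% | 28.4% |
| 80% | 75% | 16% vs 15% | 3.0% |
| 60% | 20% | 12% vs 4% | 67.2% |
| 60% | 50% | 12% vs 10% | 5.8% |

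A definition that ignores product use gives 1.8%.

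**(b) NRT truly better, 35% vs 20%, with vN = 20%.** The scored NRT rate is 0.35 × 0.20 = 7%. JUUL is still declared superior 89.8% of the time if vJ = 100% (20% vs 7%), 64.0% if vJ = 80% (16% vs 7%) and 25.4% if vJ = 60% (12% vs 7%).

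**(c) Planning rates, JUUL 35% vs NRT 20%** (80.3% under a symmetric definition)

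| vJ | vN | Scored JUUL vs NRT | JUUL declared superior |
|---|---|---|---|
| 100% | 50% | 35% vs 10% | >99.9% |
| 100% | 75% | 35% vs 15% | 97.7% |
| 80% | 50% | 28% vs 10% | 97.6% |
| 80% | 75% | 28% vs 15% | 74.9% |
| 60% | 50% | 21% vs 10% | 70.7% |

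**Direction.** Scored minus true difference = (pJ·vJ − pN·vN) − (pJ − pN) = pN(1 − vN) − pJ(1 − vJ). At equal true abstinence this favours JUUL whenever vJ > vN. At 35% and 20% with vJ = 80%, it is zero when 0.20(1 − vN) = 0.35 × 0.20 = 0.07, so vN = 65%. With vJ = 60%, it is zero when 0.20(1 − vN) = 0.14, so vN = 30%. The clause favours JUUL below those shares. This rule concerns the difference, not the rejection probability: 28% vs 13% keeps the 15-point difference but gives 87.8%.

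**Sensitivity to sample size.** Taking 20% off 420 leaves 336, or 168 per arm, rather than the 300 in E.1. At 168 per arm, 20% vs 4% gives 99.6%, 16% vs 10% gives 31.8%, 28% vs 15% gives 79.9% and 35% vs 20% gives 84.7%. The pattern is the same.

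**The case against.** The strongest reply is that the investigators meant NRT use to count for the NRT arm and left a few words out of one sentence. Hypothesis 2, section G.6 and the abstinence-based 20% all point that way. This is plausible, but E.1 repeats the e-cigarette-only wording and no section gives an NRT scoring rule, so the documents do not settle it.

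A second reply is that this is a switching trial, so e-cigarette use belongs in the endpoint. That is coherent within the JUUL arm and for Aim 3. It does not justify the clause in a test of superiority over NRT.

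Third, NRT participants may vape. Only current daily e-cigarette users are excluded, past regular use is a stratification factor, and no text forbids vaping. The calculation allows for this. The shares are unknown, and scenario (b) reverses the planning rates, so the figures show what the rule can do rather than a measured bias.

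Fourth, other outcomes avoid the clause. This is true of cigarettes per day in Hypothesis 1b. It is less clear for Hypothesis 2, which ties iCO change to the degree of substitution and so inherits the scoring question. Neither repairs the primary endpoint.

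Part of the text around section C was not available to this review. An endpoint definition there is unlikely but cannot be excluded.

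**Conclusion.** The concern holds: the primary endpoint is wrong as written and must be corrected. Read literally, it scores NRT-arm cessation without vaping as failure, which contradicts Hypothesis 2, section G.6 and the basis of the NRT planning rate.

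The size of the distortion is not established. Under the assumed shares with equal true abstinence, the chance of a false finding for JUUL runs from 1.8% to more than 99.9%. At the planning rates, the chance of declaring JUUL superior moves from 80.3% to anywhere between 70.7% and more than 99.9%, so the clause can also cost JUUL power. These figures assume Fisher's test with 150 analysed per arm. The logistic regression in E.2 would use the same scored outcome and inherit the same problem. Successes in the JUUL arm would still be CO-verified.

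**What to change.** Before anyone sees outcome data by arm, define the endpoint identically in structure for both arms. Keep the seven-day cigarette and CO criteria, and state one of two options.

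- **(i) Drop the product-use clause.** Cigarettes and iCO are already collected daily in both arms, so no new data are needed. The primary outcome then becomes verified near-abstinence from cigarettes rather than switching. Where few NRT abstainers vape, the comparison becomes less favourable to JUUL.
- **(ii) Require reported use of the assigned product in each arm.** This stays closer to switching, but two points must be settled first.
  - *NRT capture.* Confirm that NRT use is recorded for the same seven days. Table 2 shows no NRT item in the daily diary. Section H.1 says the EMAs cover nicotine products, the Surveillance Phase text says NRT use is tracked, and NRT Use Evaluation and TLFB are listed at weeks 8 and 12.
  - *Week 12.* Neither product is supplied in weeks 9–12, so an abstinent participant who has finished the supply would fail unless a rule says otherwise.

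  Some distortion remains if product use among abstainers differs by arm. At equal 20% abstinence, shares of 80% and 60% give 16% vs 12%, and JUUL is declared superior 13.1% of the time.

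Report the option not chosen, and e-cigarette-specific switching, as secondary outcomes. Align sections A, D.3, E.1, E.2 and G.6. State which definition Aim 2 uses, and which Aim 3 uses where it compares changes that "differ between those who achieve complete (vs. partial or no) substitution". State that the 35% JUUL switch rate is assumed to carry over; power is then 80.3% by Fisher's test with 150 per arm.

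The cost is rewording and approvals, plus, for option (ii), a check of the forms and a week-12 rule. Under D.2 (Regulatory Issues), the NIDA Program Officer must approve a protocol change. Prior FDA, NIDA and IRB approvals are needed if it may affect scientific soundness.

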Immediately following the baseline assessment, participants will be randomized to one of two arms for a period of 8 weeks: JUUL or NRT. Randomization will occur using a stratified block-randomization procedure with small, random sized-blocks. Randomization will be stratified by sex, education level (high school or less, GED, or greater than GED/High School), location and EC regular use history (ever at least once weekly for a month). Consistent with our previous and ongoing switching studies^{10,75,107}, participants will be instructed on how to use the JUUL, provided a starter kit (device and a charger) as well as pods initially at a 1:1 level based on established baseline smoking rate. Given JUUL pods, if completely consumed, have been found to excrete mean total nicotine equivalents associated with consuming 91% of a pack of cigarettes. We will assume that most pack a day smokers will require no more than one pod per day. The amount provided to participants will be documented and tracked throughout the study. Provision of additional pods will be titrated up or down based on use. All products will be given to participants in their original packaging and at no cost. Consistent with previous QL studies, participants in the NRT arm will be provided patch and lozenge (2 or 4 mg); for the nicotine patch, dosing will be determined by reported cigarettes per day. Specifically, for participants smoking 5-10 cigarettes per day they will be provided with 4 weeks of the 14 mg and 4 weeks of the 7 mg nicotine

Switching to a Vaping Device: Evaluating Risk Reduction among Quitline Treatment Failures

patches; participants smoking 11+ cigarettes per day will be provided 4 weeks of 21mg, 2 weeks of 14mg, and 2 weeks of 7mg nicotine patches. All NRT will be provided for up to 8 weeks.

Randomized Product Trail Phase

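### The Fisher test named for the week-8 primary outcome uses none of the four stratification factors, and the adjusted model for the same outcome leaves them optional

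*Combined protocol and SAP*

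**What the plan says.** E.1 (Power Analysis) states: "Complete substitution of combustible cigarettes for EC products is the primary outcome of the study". It compares the arms "at the end of the product trial phase (8-week follow-up) using the Fisher's exact test", but bases the power statement on another test, "for a two-sided .05 level chi-squared test".

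D.2 (Baseline Phase) specifies small blocks of random size: "Randomization will be stratified by sex, education level (high school or less, GED, or greater than GED/High School), location and EC regular use history". The screening section of D.2 also lists four factors.

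E.2 (Data Analytic Plan, Hypothesis 1a) analyses the same outcome at weeks 8 and 12 by logistic regression. Age and gender are given as examples of covariates, and the list ends "number of cigarettes per day and/or randomization stratification factors". A GEE across visits follows, with no covariates stated. Neither section says whether Fisher, chi-squared, the logistic model or the GEE is the primary analysis.

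**The concern.** Stratifying on factors related to the outcome makes the arms more alike than chance would. An analysis that ignores those factors still charges for chance imbalance that the design has removed, so it rejects too rarely under the null and loses some power. Fisher's test is conservative even without this, because its p-value is discrete.

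The point does not turn on which analysis is called primary. Fisher uses no covariates. The logistic model may include the strata or not. The GEE is silent. Choosing among them, and choosing the covariates, after the data are seen would also be an avoidable freedom on the main comparison.

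**Working it through.** **Inputs from E.1.** JUUL: "we estimate that the percent of complete substitution will be 35" per cent. NRT: "we will conservatively assume a NRT substitution rate of 20" per cent. Two-sided alpha is 0.05 and 300 are analysed. I take 150 per arm; no ratio is stated, but the per-group figure implies 1:1. I also show 168 per arm, because 420 × 0.80 = 336.

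**Plan's own figure.** The plan says: "A sample size of 300 will provide >80% power to detect a difference in complete substitution between JUUL and NRT groups". For chi-squared, power = Φ[(d − 1.96·SE0)/SE1], with:
- d = 0.35 − 0.20 = 0.15
- SE0 = √(2 × 0.275 × 0.725/150) = 0.0516
- SE1 = √((0.35 × 0.65 + 0.20 × 0.80)/150) = 0.0508

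This gives Φ(0.963) = 83.2%, so the plan's figure reproduces.

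**Fisher against chi-squared.** Exact enumeration of all 2×2 tables, with equal arms; size is at a common rate of 27.5%:

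| Per arm | Fisher power | Fisher size | Chi-squared power | Chi-squared size |
|---|---|---|---|---|
| 150 | 80.3% | 3.7% | 83.5% | 5.0% |
| 168 | 84.7% | 3.8% | 87.3% | 5.0% |

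The cost of Fisher alone is 83.5 − 80.3 = 3.2 points at 150 and 87.3 − 84.7 = 2.6 at 168. No covariate is involved. The cost depends on exactly equal arms: the same enumeration with 151 on JUUL and 149 on NRT gives Fisher 81.8% power and 4.3% size, against 83.5% for chi-squared.

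**Adjustment alone.** Multiply both variances by (1 − R²), where R² is the share of outcome variance explained by the strata and cigarettes per day. The documents give no value, so R² is assumed:

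| R² | 150 per arm | Gain | 168 per arm | Gain |
|---|---|---|---|---|
| 0 | 83.22% | – | 87.18% | – |
| 2% | 83.96% | 0.74 | 87.83% | 0.65 |
| 5% | 85.08% | 1.86 | 88.80% | 1.62 |
| 10% | 86.92% | 3.70 | 90.39% | 3.21 |

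**Simulation check.** 150 per arm on average, 16 strata, blocks of 2 or 4, and 4,000 runs per setting. Each of the four factors and cigarettes per day has the same assumed odds ratio (OR), per SD for cigarettes per day:

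| OR | Fisher | Chi-squared | Adjusted logistic |
|---|---|---|---|
| 1.3 | 81.4% | 84.1% | 84.9% |
| 1.5 | 80.2% | 82.4% | 84.0% |
| 2.0 | 82.9% | 85.0% | 88.9% |

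Under the null, Fisher's size was 4.2% when the covariates had no effect and 3.3% at OR 2.0. Chi-squared fell from 5.2% to 4.1%. The adjusted model stayed at 5.1% to 5.2%. The fall for the two unadjusted tests is the effect of ignoring prognostic strata; the rest of Fisher's shortfall is discreteness.

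**The case against.** The strongest reply is that the Fisher sentence sits in the power section and may only describe the sizing comparison, while E.2 is the analysis plan and already provides an adjusted model. That model names cigarettes per day and gender, and gender corresponds to one stratification factor. E.1 also calls the sample size conservative and expects the longitudinal models to add power. Fisher's test is valid after stratified randomisation, and its power at 150 per arm still exceeds 80%.

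Most of this stands. A reader might infer that the plan has no covariate adjustment; E.2 shows otherwise. But E.1 presents Fisher as how the primary outcome will be compared, E.2 does not say that its model supersedes it, and the E.2 list commits to no covariate. Education, location and e-cigarette history can all drop out under its wording. The power margin is also thin: E.1's 186 per group less 20% is 148.8, and exact Fisher power at 149 equal per arm is 79.9%.

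**Conclusion.** The point holds as a gap in pre-specification with a modest efficiency cost. It is not an error that threatens validity. At the plan's rates, Fisher costs about 3 points of power against chi-squared with equal arms, and nearer 2 when arm sizes differ slightly. Adjustment would add roughly 1 to 4 points if R² is 2% to 10%.

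Two stronger readings are not supported:
- **Ignoring the strata costs five or more points.** A total gap of that size from Fisher to the adjusted analysis needs an R² of about 5% to 6% at 150 per arm, or 7% to 8% at 168, and much of it would still be Fisher's discreteness. In the simulation the total was 3.5, 3.8 and 6.0 points at odds ratios of 1.3, 1.5 and 2.0. The documents give no prognostic strength for any covariate.
- **The confidence intervals are too wide.** The plan attaches no interval to Fisher's test. What can be shown is a type I error below the nominal 5%.

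**What to change.** In E.1 and E.2, name one week-8 primary analysis. One suitable choice is logistic regression of complete substitution on arm, with the four stratification factors as randomised and baseline cigarettes per day, reported as a standardised risk difference with 95% CI. That keeps the result on the scale of the 35% versus 20% assumption.

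- Delete *such as* and *and/or* from the Hypothesis 1a covariate list, and use the same fixed list in the GEE.
- Enter the factors as main effects, not stratum cells. With three education levels and only two locations there would be 2 × 3 × 2 × 2 = 24 cells, and about 0.275 × 300 ≈ 82 participants with the outcome.
- State which e-cigarette factor was used to randomise. The screening section of D.2 says ever use; the Baseline Phase section says regular use. The covariate must match the one used.
- Keep Fisher's test as a sensitivity analysis, and tie the power statement to the named analysis.

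The cost is a few sentences, with no new data or participants. The downside is a small loss of simplicity.
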